1.3 Altered Fractionation in Breast Cancer

In standard chest wall irradiation, daily fraction sizes of 180 cGy or 200 cGy are commonly used and are described as conventional or standard. The rationale for conventional fractionation and the relationship between fraction size and tissue response is well described by the α/β ratio in the linear quadratic model of fractionation sensitivity [37]. In this empiric model, “late-reacting” normal tissues such as fibroblasts and neurons have a low α/β ratio (2-5 Gy) and are very responsive to increases in fraction size, while “acutely-reacting” normal tissues such as intestinal epithelium have a high α/β ratio (>7 Gy) and are less responsive to changes in fraction size. The biological effect of a given fractionation scheme size is related to the α/β ratio by the equation:

$$\text{Effect} = E = n(\alpha d + \beta d^2) \text{ where}$$

d = dose/fraction

n = # of fractions

Although relatively high cumulative doses of radiation are needed for tumor control, the daily fraction size has to be respectful of the fraction sensitivity of normal tissues in the treated volume. Accounting for these assumptions, increases in fraction size have to be compensated for by reductions in cumulative radiation dose, which typically are insufficient for tumor control. As a result, daily fractions of 1.8 to 2 Gy are delivered over 4-6 weeks to reach a cumulative dose of 45-60 Gy. In vitro experiments in human breast carcinoma cell lines have suggested an α/β ratio of about 4 Gy [38, 39]. In 1986 Royal Marsden Hospital and the Gloucestershire Oncology Centre collaborated in a prospective trial evaluating 3 breast fractionations. [1, 40]

50 Gy in 25 fractions over 5 weeks

39 Gy in 13 fractions (3.0 Gy/fx) over 5 weeks

42.9 Gy in 13 fractions (3.3 Gy/fx) over 5 weeks.

In 1999, after over 1400 patients had been enrolled, the trial design was expanded into a multi-institutional trial and patient data from the earlier study was rolled into what became Start A, with the 13 fraction regimen changed to 3.2Gy/day for 41.6Gy [5]. A total of 2236 women were randomized to one of three arms between 1986 and 1999:

The overall treatment time was kept constant in all three arms. The primary endpoint was late breast change. Local control was a secondary endpoint. The protocol did allow treatment of regional lymph nodes (supraclavicular and axillary) with additional radiation fields, and these were used in 20% of the patients. Fourteen percent of patients received CMF chemotherapy. It must be noted that none of the 290 patients who were treated to the axilla and supraclavicular areas developed brachial plexopathy in the initial publication. At 10 years, however, there was one reported case of plexopathy in the high dose 41.6Gy arm. A major limitation of the study is the use of a conventionally fractionated boost of 14 Gy in 7 fractions. How this boost interacted with the altered fractionation effects is unclear. It also unfavorably impacts the convenience of the experimental arms.

Running in parallel to Start A, Start B was an accelerated hypofractionation trial comparing 50Gy in 2Gy daily fractions for 5 weeks versus 40Gy delivered in 2.67Gy daily for 15 days. Results were described above. These trials are both limited in their applicability as only small proportion of patient were treated post mastectomy and with regional nodes radiated, in addition to the fact that chemotherapy was mostly CMF based and radiation centers were allowed to use 2D planning and lower energy cobalt.

Again in the setting of an intact breast, NCI Canada randomized 1234 patients (1993-1996) with T1 and T2 tumors with negative margins and pathologically negative nodes (on level 1 and 2 dissection) to:

1. 50 Gy in 25 fractions (2 Gy/fx) over 35 days or
2. 42.5 Gy in 16 fractions (2.66 Gy/fx) over 22 days [41].

Dose was prescribed to the 1/3rd point, and homogeneity within 7% was required. Lumpectomy bed boost and treatment to regional draining lymph nodes was not allowed. With a median follow-up of 9.3

years, there was no difference in local regional recurrence, OS and DFS. Cosmesis was identical with excellent or good scores at 3 and 5 years in 77% of patients in both groups. Toxicities were comparable. Grade 2 and 3 toxicities were negligible. At 5 years, 87% of women in the experimental arm had no skin toxicity, and 66% of women had no subcutaneous toxicity, compared with 82% and 60% in the control arm, respectively. A major limitation of the Canadian study is the lack of a lumpectomy boost, which has been shown in prospective randomized trials to significantly improve local control [42, 43]. The patients eligible for the study had low risk for disease recurrence, limiting the general scope of the results. In addition, the regional nodes were untreated, making the safety of irradiating a larger volume unclear.

Rodger, et al. at the Western General Hospital, Edinburgh, UK, published a retrospective review of late effects in post-mastectomy patients before and after a policy change in their department, changing from 4.5 Gy times 10 fractions over 4 weeks to 2.25 Gy times 20 fractions, after a simple mastectomy. All patients were treated to the regional lymph nodes, and dose to supraclavicular and axillary areas was 4.25 Gy times 10 in the hypofractionation arm. 484 patients were treated with the 10 fraction regimen during 1/1979 and 3/1982, while 289 patients were treated with the 20 fraction regimen from 4/1982-12/1984. There were more late effects in the hypofractionation arm: Grade 3-4 skin effects on the chest wall 29/79 (37% vs. 0 (0/92)), subcutaneous effects 66% vs. 10% on the chest wall and 29% vs. 14% in the axilla. Grade 2-3 arm edema was also higher 29% vs. 14%, as were rib fractures 52% vs. 11%. Two plexopathies were seen in each group. The two regimens produced equal disease control. Although not a randomized comparison, the outcomes reported in this study are instructional, especially in light of the linear-quadratic model, which was not available to the clinicians in Edinburgh. Assuming an α/β ratio of 4 Gy, the patients received a whole breast dose equal to 58 Gy in 2 Gy fractions, ($Gy4=87.65$, while 50 Gy in 2 Gy= 75 Gy4). It would appear from this analysis that the patients were over treated.

This 16 day radiation treatment design is supported in its safety and efficacy through randomized trials in early stage breast conservation, and will reduce cost while likely improving patient satisfaction for women requiring PMRT. The promise of short-course PMRT lies in the added convenience it may offer to patients who otherwise may not be able to receive PMRT, and it may also allow earlier sequencing of PMRT with systemic chemotherapy. Although sequencing seems to be unimportant in the context of breast preservation [44], it may be important in women at higher risk for locoregional recurrence. In the trial, we will allow adjuvant chemotherapy to be delivered before or after PMRT. Given the excellent cure rates and low morbidity with current adjuvant radiation therapy technique and fractionation, it is only natural that subsequent improvements in the field take convenience and economic impact into account.

1.4 Patient Satisfaction and Well-being as Patient Reported Outcomes (PROs)

The assessment of patient-reported outcomes (PROs) in clinical research provides important insight into how therapies impact the daily lives of patients. There is a growing recognition that patient-reported endpoints are critical in oncology trials, particularly when cosmesis and toxicity are likely to be different in the treatment arms. Patient-reported adverse event collection has been shown to be more thorough than collection by provider-report, with consistent underreporting of side effects by providers.[69] Patient-reporting of health-related quality of life has become the gold standard in part because providers have been found to underestimate the pain and distress their patients are experiencing. [70-72]

In a trial of different radiation schedules, in which cosmesis may be substantially different in the two arms of the study, patient-reported satisfaction and well-being are particularly important. Although short-term differences between the treatment arms may be momentarily relevant to patients, the long-term cosmetic outcomes are most critical, so we have chosen to collect these data at 24 months (and compare to pre-treatment measures). In order to avoid burdening patients, we will not survey them for satisfaction or well-being in between these time points.

1.4.1 Lymphedema Background

Patient-reported outcomes such as symptom assessment and QOL can serve multiple purposes, including acting as validation measures of treatment efficacy in the context of clinical trials and serving as reference points for clinical decision-making when modest differences in survival are anticipated among various treatment modalities [48-50]. It is possible in this trial that while the treatment outcomes with respect to disease recurrence are equivalent that the morbidity associated with each of the treatment arms is not the same. In this setting, it is critical that a comprehensive assessment of treatment-associated morbidity be performed in order to represent the entirety of the treatment experience. As the contemporary treatment for breast cancer evolves, it is important to examine the morbidity associated with various treatment regimens.

Arm Lymphedema: Arm lymphedema is one of the most dreaded complications of breast cancer treatments, in that it often causes physical discomfort, psychological distress, functional impairment, change in body habitus and self-image, chronic disability, and diminished QOL [51-55]. In addition, lymphedema incurs significant financial costs, both to the affected individual and to the national and international health care delivery systems. In a review of the published literature concerning breast cancer treatment-related lymphedema, Erikson et al. concluded “there is need for better understanding of the prevalence and morbidity of arm edema in population-based studies” [56]. As the contemporary treatment for breast cancer evolves, it is particularly important to examine the incidence of lymphedema and associated symptoms.

Of those treated for breast cancer, it has been reported that the incidence of lymphedema varies widely depending on the criteria applied [57]. The most common estimates reported are 20 to 40% for women undergoing axillary lymph node dissection [58-63]. The challenges related to lymphedema measurement, diagnosis, and follow-up are cited as the primary reasons for these large discrepancies in reported lymphedema incidence.

Armer et al. have reported that in a cohort of 211 breast cancer participants with 30 months post-treatment follow-up who were assessed using perometry, circumferences, and symptom assessment that the incidence of lymphedema ranged from 41 to 91% with 2 cm being the highest estimation method and symptoms the lowest [57, 64].

In a recent report from the NSABP B-32 trial, arm volumes were assessed over 3 years following axillary lymph node dissection (n=1,975) or sentinel lymph node biopsy (n=2,006) using water displacement techniques. In this study, arm volume differences were only noted for 14% (compared to 8.6% at baseline) of patients undergoing axillary lymph node dissection and 7.5% (compared to 8.0% at baseline) of those undergoing sentinel lymph node biopsy. [65] Numbness and tingling were the two symptoms assessed in this study, as well as shoulder abduction. Radiation to the axilla was reported to increase the risk for residual arm volume difference (OR = 3.47) however the actual number of patients treated with XRT was very small (ALND Group: n = 22, 1.1% and SLND Group: n=13, 0.7%). While the reported incidence of lymphedema following sentinel node biopsy concurs with other studies, the reported incidence of limb volume differences following axillary dissection was lower than that reported in the majority of studies. Although this study provides some paired symptom data with objective measures of lymphedema, key symptoms of lymphedema (i.e. heaviness and swelling) were not included, and the very small number of patients treated with XRT demonstrates the gap in knowledge that we propose to address in the current trial.

Whether or not radiation treatment to the axillary lymph nodes or breast/chest wall increases the risk of developing lymphedema and/or associated symptoms is still unresolved. A number of studies have reported that there is no association. [60, 66]

It is even more unclear whether or not axillary XRT alone (or following sentinel lymph node biopsy) increases the risk of lymphedema. Therefore, in the setting of this proposed breast cancer treatment trial, it is imperative to obtain objective clinical assessment data and to use validated lymphedema symptom assessment tools to inform future decision-making related to these cancer

therapies. The clinical and patient-reported lymphedema assessments are more thoroughly described in [Section 10.5](#).

1.4.2 Breast Q Survey

We will be using the Breast Q survey tool to assess patient satisfaction and well-being. [81-83] This tool has been validated for use in patients before and after mastectomy with reconstruction to assess well-being and patient satisfaction with results, and is provided free of charge for academic research. Cronbach's alphas for the scale range from 0.81 to 0.98, and the BREAST-Q has test-retest reliability, demonstrated by an intraclass correlation coefficient ranging from 0.85 to 0.987.[73]

1.4.3 Was it Worth It Questionnaire

The Was It Worth It instrument was developed to learn more about the experience of patients participating in clinical trials. It is comprised of four brief questions, and it has also been called the "Trial Satisfaction" survey.[74] Although formal validity and reliability data for this instrument are not yet available, multiple cooperative group studies have used it to measure how satisfied patients end up with their decision to enroll on a clinical trial.[75-79]

1.5 Photographic Cosmetic Assessment

There are no validated photographic assessment tools in patients with breast reconstruction. The EORTC Breast Cosmetic Rating system is a digital photographic method that has been utilized in prior radiation studies and shown to be reliable and valid in detecting effects of radiation morbidity. [45-47] This method compares the radiated breast with the contralateral untreated side and evaluates: Size, shape, location of the areola/nipple, appearance of the surgical scar, skin pigmentation changes, presence of telangiectasia and a global cosmetic score based on all of the factors. Characteristics are graded on a four-point scale: 0, excellent or no difference; 1, good or small difference; 2, fair or moderate difference; and 3, poor or large difference.

1.6 Study Hypotheses

- Short course hypofractionated radiation has a non-inferior reconstruction complication rate compared to standard fractionated radiation.
- Short course hypofractionated radiation offers reconstructed women better cosmesis, reduced lymphedema, and quality of life with a similar rate of cancer recurrence and treatment toxicity.

2.0 OBJECTIVES

2.1 Primary Objective

To evaluate whether the reconstruction complication rate at 24 months post radiation is non-inferior with hypofractionation. Complications will include those listed in [Section 10.1](#).

2.2 Secondary Objectives

- 2.2.1** To evaluate the incidence of acute and late radiation complications based on CTCAE 4.0 toxicity.
- 2.2.2** To evaluate the local and local regional recurrence rate.
- 2.2.3** To compare reconstruction complication rates based on reconstruction method (autologous +/- implant vs implant only) and timing of reconstruction received (immediate vs. intent for delayed).

2.3 Photographic Cosmetic Assessment

- 2.3.1** To evaluate reconstructed breast photographic cosmetic scores with hypofractionated radiation compared to standard fractionation 24 months after radiation.
- 2.3.2** To evaluate reconstructed breast photographic cosmetic scores 24 months after radiation based on the method and timing of reconstruction received.

2.4 Lymphedema Assessment

- 2.4.1** To estimate the incidence of arm lymphedema by treatment arm.

2.5 Patient Reported Outcomes (PRO) Objectives

- 2.5.1** To compare physical well-being, psychosocial well-being, sexual well-being, satisfaction with breast/nipples/abdomen, and satisfaction with overall outcome between the treatment arms at 24 months after radiation.
- 2.5.2** To estimate patient satisfaction with trial participation by treatment arm as measured by the Was It Worth It Questionnaire at 24 months after radiation.

2.6 Economic Analysis

- 2.6.1** To compare the direct and indirect patient costs for radiation therapy by treatment arm.
- 2.6.2** To compare patient reported total health care service utilization 12 months after the completion of radiation.
- 2.6.3** To compare the economic impact of treatment.

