12.2 Sample Size, Accrual Time and Study Duration

Our target sample size will be 792 evaluable patients (396 in each arm). To account for 10% drop-out due to cancellations or protocol deviations, our target accrual is 880 patients (440 per arm) (90% of 880 is 792).

The study design is a randomized, un-blinded, non-inferiority trial. It is assumed that the two-year breast reconstruction complication rate for the control arm (Arm 1: standard fractions) is 25%. Other assumptions for the sample size determination include:

- α (one-sided) = 0.025
- power = 90%
- non-inferiority margin: the absolute increase in the proportion of patients who experience
- a breast reconstruction complication within two-years is 10% above that of the control arm.
- one interim analysis (when 30% of the information is obtained) for futility

Under an alternative hypothesis that the true rates in the two arms are equal, a sample size of 792 (396 per arm) evaluable patients would give us 90% power to reject the null hypothesis of inferiority. The final analysis will take place after all patients have reached two years post-radiation. The anticipated accrual period is approximately 30 months, and the total study duration is approximately 60 months. We anticipate being able to accrue approximately 30 patients per month based on our best estimate extrapolated from recently closed intact breast trials looking at similar fractionations. It should be noted that if we instead assumed a complication rate of 50% in the control arm (the most statistically conservative, in terms of sample size), the above sample size would still give us approximately 80% power to reject the null hypothesis of inferiority (again with one-sided α of 0.025).

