12.4.5 Economic Analyses

Direct costs of medical care to each patient will be estimated using utilization information from the health care expense survey and the health care utilization survey, along with publicly available Medicare reimbursement rates. In particular, based on the reported number of outpatient visits to the radiation oncologist, medical oncologist, surgeon who performed mastectomy, plastic surgeon or physical therapist, and the number of visits to the emergency room, the number of hospital admissions (and the days per each hospital admission), and the number of surgical procedures to breast reconstruction (along with the names of the procedures), Medicare reimbursement rates can be used to estimate what the direct cost to each patient would be if that patient were covered by Medicare. Generalized linear models will then be used to model these costs as a function of treatment, time on study, and all available baseline patient characteristics to assess the extent to which estimated direct cost is impacted by the type of radiation dosing. Given the well-known fact that healthcare costs are typically highly skewed, regression models will employ the appropriate distribution and transformation link. We will also assess the degree to which indirect costs differ across the two treatment arms. Specifically, using information from the phone survey, along with information on work status prior to breast cancer diagnosis, the average number of days worked per week (at baseline), and the average number of hours worked per day (at baseline), we will estimate the hours of work missed and the total distance traveled to receive radiation treatment for each patient. These two endpoints will be modeled (separately) as a function of treatment, time on study, and all available baseline patient characteristics to assess the extent to which the treatment arms differ with respect to indirect cost.

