In addition to using them to estimate direct costs, the health care utilization measures (number of outpatient visits to the radiation oncologist, medical oncologist, surgeon who performed mastectomy, plastic surgeon, physical therapist; the number of visits to the emergency room, the number of hospital admissions, the days per each hospital admission, and the number of surgical procedures to breast reconstruction) will be compared (separately) across the two dosing arms. Given that these outcomes are counts, appropriate count regression models (e.g., poisson regression, negative binomial regression or zero-inflated negative binomial regression) will be used to account for any residual imbalance between the study arms following randomization.

EQ-5D survey results for the baseline and follow-up will be presented in three ways: (i) the descriptive system on the 5 dimensions will reflect the patients general health profile; (ii) EQ-VAS will represent patients' self-reported health status; and (iii) the summary measure of generic health status in terms of EQ-5D-3L index value. In order to obtain the last measure, EQ-5D responses representing specific health state will be converted to a single index value using the EQ-5D-3L value sets for the U.S. This, along with the survival data, will then be used to estimate the effectiveness measure in our cost-effectiveness analysis, that is, quality adjusted life year or QALY. Mean QALYs between interventions will be compared using two-sided t-test. Cost-effectiveness will be assessed and compared in terms of incremental cost-effectiveness ratio or ICER, that is, US dollars per QALY between the interventions. Costs associated with each of the interventions will be estimated. For healthcare utilizations mentioned above, costs will be imputed from the literature. Extensive sensitivity analyses will be conducted to document sensitivity of the final results to any of the imputed cost parameters.

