APPENDIX VIII PATIENT HEALTH CARE UTILIZATION DIARY

This diary is for your use to record your visits to health care facilities to help us complete a questionnaire 1 year after radiation. We would like to capture all visits to any medical facility related to your healthcare in the 1 year after completing radiation.

Types of visits to record:

Clinic visits to radiation oncology
 Clinic visits to medical oncologist
 Clinic visits to surgeon who performed mastectomy
 Clinic visits to plastic surgeon
 Visits to emergency room
 Visits to physical therapist
 Other health care services used that are not listed

Hospital admissions, also record days per each hospital admission
 Surgical procedures to breast reconstruction, also record the name of each procedure

	Date	Type of visit	If hospital admission, number of days
1 Month after RT			
2 Months after RT			

	Date	Type of visit	If hospital visit, number of days
3 Months after RT			
4 Months after RT			
5 Months after RT			
6 Months after RT			
7 Months after RT			

	Date	Type of visit	If hospital visit, number of days
8 Months after RT			
9 Months after RT			
10 Months after RT			
11 Months after RT			
12 Months after RT			

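### Objective 2.6.2 asks about total health-care use, but 12.4.5 forms no patient-level utilisation total, and its days-per-admission comparison covers only admitted patients and can favour the arm with more hospital days.

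*Combined protocol and SAP*

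**What the plan says.** Section 2.6 lists three economic objectives. The second, 2.6.2, is "To compare patient reported total health care service utilization 12 months after the completion of radiation". Patient costs are the separate objective 2.6.1.

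The utilisation analysis is in 12.4.5. Its list opens with "number of outpatient visits to the radiation oncologist, medical oncologist, surgeon who performed mastectomy, plastic surgeon, physical therapist", adds emergency room visits, and closes with "the number of hospital admissions, the days per each hospital admission, and the number of surgical procedures to breast reconstruction) will be compared (separately". That makes nine items. The model statement is "Given that these outcomes are counts, appropriate count regression models", with Poisson, negative binomial and zero-inflated negative binomial given as examples. The section defines no sum, names no lead item, and gives no rule for length of stay in patients without an admission.

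Earlier in 12.4.5 the same items are priced at Medicare rates to give a direct cost per patient: "Generalized linear models will then be used to model these costs as a function of treatment".

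The source is the diary in Appendix VIII. It asks for each visit by type, for "Other health care services used that are not listed", and for "Hospital admissions, also record days per each hospital admission". Section 10.7 has patients keep it from the end of radiation to the 12-month visit.

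**The concern.** There are three linked gaps.

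First, the objective names a total and the analysis section does not compute one. Nine results then stand side by side, with no statement of which of them, or what combination, answers 2.6.2.

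Second, a service the patient is asked to record, the other-services entry, is neither among the nine items nor in the list used for costing. Even a reader who added up the nine items would not have total use.

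Third, days per admission has the admission as its unit. Admission happens after randomisation and may depend on the radiation schedule. The comparison is then between two groups selected by a possible effect of treatment, so randomisation no longer protects it. An arm that generates extra short admissions lowers its own average stay, and the item can read as an advantage for the arm that used more hospital days.

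What is at stake is the answer to an economic objective, not the primary conclusion.

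**Working it through.** The plan gives no sample size, power, alpha, admission rate or length of stay for 2.6.2, so there is no stated figure to reproduce.

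**Item count (12.4.5).** Five outpatient visit types + emergency room visits + admissions + days per admission + reconstruction procedures = 9. Setting this list against Appendix VIII, other services is the one diary category with no counterpart.

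**When the two hospital measures disagree.** Let p be admissions per randomised patient and d the mean days per admission.

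- Days per randomised patient = p × d.
- Days per admission favours arm B when d_B < d_A.
- Arm B nevertheless uses more days when p_B/p_A > d_A/d_B.

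Both hold whenever B's stays are shorter and its excess of admissions outweighs the shortening.

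**Illustration 1 (all rates and stays assumed).** Arm 1: 10% admitted, mean 4 days. Arm 2: the same 10%, plus a further 10% with a mean of 2 days.

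- Days per randomised patient: 0.10 × 4 = 0.40 v 0.10 × 4 + 0.10 × 2 = 0.60, which is 50% more in Arm 2.
- Days per admission: 0.40/0.10 = 4.0 v 0.60/0.20 = 3.0, which favours Arm 2.

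**Illustration 2 (assumed).** At 396 per arm, with A 10% × 6 days and B 20% × 4 days, there are 40 and 79 admissions.

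- Total days: 240 v 316, or 0.61 v 0.80 per randomised patient (ratio B/A 1.32).
- Days per admission: ratio 4/6 = 0.67.

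**How often this would be seen.** Illustration 1 was simulated with stays of 1 + Poisson, at most one admission per patient, and robust standard errors. The size came from "Our target sample size will be 792 evaluable patients (396 in each arm").

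- The per-admission test significantly favoured Arm 2 in about 85% of trials.
- The admission count was significantly worse for Arm 2 in about 97%.
- The favourable stay result without the adverse admission count occurred in about 2%.

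Varying the assumed extra admissions gave:

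| Extra admissions in Arm 2 | Per-admission test favours Arm 2 |
|---|---|
| 10%, 2 days | about 85% |
| 10%, 3 days | about 34% |
| 10%, 4 days | about 3% |
| 5%, 2 days | about 46% |

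In the last row, about one trial in five gave the favourable stay result without a significant admission count.

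**The case against.** The strongest reply has four parts.

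**Total may mean across all service types.** Section 2.6.2 does not define the word, and 12.4.5 does compare every listed type. The direct-cost model is also a patient-level aggregate in which extra admissions and longer stays count against the arm that has them. A reader might infer that 2.6.2 goes wholly unanswered, and the documents do not support that. What stands is narrower. The aggregate is a cost, it also uses the expense survey covering the radiation period, and it matches 2.6.1. The procedure-code submission in 10.7 likewise feeds a cost estimate, and it is not patient-reported.

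**Days per admission may be loose wording for a per-patient count.** It echoes the diary's recording instruction, and zero-inflated models suit a per-patient count with many zeros. That is a fair reading. But the text assigns no zero to patients never admitted, and naming a zero-inflated model does not define the outcome.

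**Admission counts are compared too.** A reader might infer that the plan would report heavier hospital use as a benefit. In Illustration 1 that would nearly always mean ignoring an adverse result beside it. What stands is that the plan could yield two significant and opposite results, with no analysis that reconciles them.

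**Multiplicity.** A reader might conclude that the nine tests carry a 37% false-positive risk, since 1 − 0.95^9 = 0.370. That needs independence and a 5% level for each test. The plan states no level for these comparisons, positive correlation would lower the figure, and the other secondary comparisons in 12.4 have no stated adjustment either. The point does not rest on it.

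**Conclusion.** The point holds in this form: 12.4.5 contains no utilisation total matching 2.6.2, omits the diary's other services, and includes one comparison that as worded is restricted to patients selected after randomisation. These follow from the text and need no assumed numbers. That days per admission can reverse the direction is arithmetic.

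How likely and how large a reversal would be is unknown, because the documents give no admission rates or stays. The 4.0 v 3.0 against 0.40 v 0.60 example shows direction only. The simulated frequency ranged from about 3% to about 85% as the assumed extra stays and admissions changed. The admission-count comparison and the cost model limit the damage, but neither supplies hospital days or a total of use. The primary non-inferiority conclusion and patient safety are not affected.

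**What to change.** Make these changes in 12.4.5:

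1. Replace days per admission with total inpatient days per randomised patient from the end of radiation to 12 months, set to zero where the patient was never admitted. Use the count models already named. State that an unreturned diary is missing, not zero.
2. Keep the comparison of the number of admissions.
3. Add a per-patient total of recorded contacts over the same 12 months, including the other-services entries, as the summary that answers 2.6.2. Count each episode once, so that an emergency visit leading to admission and surgery is not counted three times. The diary's dates and visit types allow this.
4. Label the item-level comparisons as supportive.

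The cost is analysis-plan wording and two derived variables from data already collected, with no new visits or forms. There are two drawbacks. The contact total gives unlike services equal weight, so a clinic visit counts the same as an admission. Inpatient days per patient is also noisier than the admission count: in Illustration 1 it was significantly worse for Arm 2 in about 52% of simulated trials, against about 97% for the count. That is the reason to keep both.
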